15.4 Sample Size Considerations

The anticipated sample size for this trial is 3,000 with approximately 420 recruited at each site over an 18-24 month period. Approximately 15-20 persons per month per site will be recruited. Recruitment may be unbalanced across the sites due to larger client volume at some sites. Sample size calculations were based on the primary outcome: sustained virologic response (SVR) defined as HCV RNA < lower limit of quantification (LLOQ) 10 to 60 weeks after completion of treatment (cure) and an intention to treat analysis. The trial is defined for superiority assessment; however, if no statistically significant difference between support strategies is detected within a specific stratum, a lesser objective of interest is non-inferiority with a pre-specified non-inferiority margin.

ELEVATED RISK STRATUM	N=1500 total (750 high intensity, 500 medium intensity, 250 low intensity)		N=1225 total (intensity, 410 intensity, 200		N=1000 total (500 high intensity, 333 medium intensity, 167 low intensity)		
SVR in PWID	RR comparing RR comparing		RR RR comparing		RR	RR comparing	
receiving	high to low	high to medium	comparing	high to	comparing	high to	
low/medium	intensity	intensity	high to low	medium	high to low	medium	
intensity			intensity	intensity	intensity	intensity	
intervention							
0.80	1.09	1.08	1.10	1.08	1.11	1.09	
0.85	1.08	1.06	1.08	1.07	1.09	1.08	
0.90	1.06	1.05	1.06	1.05	1.07	1.06	
0.95	1.04	1.03	1.04	1.03	1.04	1.04	
MINIMAL RISK	N=1500 total (750 low		N=1225 total (N=1000 total (500 low		
STRATUM	intensity, 500 medium		intensity, 410		intensity, 333 medium		
	intensity, 250 high intensity)		intensity, 200 high intensity)		intensity, 167 high intensity)		
SVR in PWID	RR comparing	RR comparing	RR	RR comparing	RR	RR comparing	
receiving low	high to low	medium to low	comparing	medium to low	comparing	medium to low	
intensity	intensity	intensity	high to low	intensity	high to low	intensity	
intervention			intensity		intensity		
0.80	1.10	1.08	1.11	1.08	1.12	1.09	
0.85	1.08	1.06	1.09	1.07	1.09	1.08	
0.90	1.06	1.05	1.07	1.05	1.07	1.06	
0.95	1.04	1.03	1.04	1.03	1.05	1.04	

Table 15.4.1. Relative risk (RR) of sustained virologic response (SVR) across stratum of risk for treatment failure (elevated and minimal risk).

[figure not shown]

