Based on preliminary data, minimal and elevated risk strata will be defined by the median of the prognostic score (estimated 1500 per stratum). However, the exact distribution will be based on the cutoff that maximizes predictive accuracy according to AUROC analysis. As such, an estimated 1000-1500 persons will be within the stratum that has the lower number of participants. **Table 15.4.1** illustrates the minimal detectable relative risks (RR) that can be detected for a range of scenarios assuming a two-sided alpha=0.05 and 80% power. The scenarios illustrate detectable effect sizes with the optimal sample size (n=3000) but also with a reduced total sample size of 2450 (assuming 1000-1225 will still be allocated per stratum).

For example, in the elevated risk stratum, assuming an SVR of 85% in those receiving the low/medium intensity intervention, a RR of 1.06 comparing SVR in those receiving the high intensity intervention to those receiving the medium intensity intervention and 1.08 comparing those receiving the high intensity intervention to those receiving the low intensity intervention can be detected if the total allocated to this stratum is 1500. Power will be slightly reduced if the total sample size in this stratum is 1000. Similarly, in the minimal risk stratum, if a 95% SVR rate is observed in those receiving the low intensity intervention, a RR of 1.03 comparing the medium intensity to the low intensity intervention and a RR of 1.04 comparing the high intensity intervention to the low intensity intervention can be detected with a sample size of 1500 per stratum. Power will be increased if a lower SVR (<95%) is observed in the comparator group.

If no difference is detected in a comparison of two arms, non-inferiority will be established if SVR in those receiving one intensity of intervention compared to another is less than 3.4% (non-inferiority with sample size of 1500 and SVR=95% in the comparison group). The margin is 4.5% if the sample size is 1000 in one of the groups. Non-inferiority margins <5% are clinically meaningful. Power for secondary outcomes of treatment completion is comparable.

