At the Entry visit, prior to randomization and treatment initiation, each participant will undergo a short survey to capture information on barriers/facilitators to treatment adherence identified in the prediction model. Responses to this survey will be captured in an eCRF and integrated with other data from the EHR. The algorithm will be used to classify persons into two strata according to their propensity for HCV treatment failure (minimal or elevated risk).

Individuals will be preferentially randomized to the support level that matches their failure risk. Those at elevated risk for treatment failure will be randomized at an allocation ratio of 3:2:1 for high, medium and low intensity support respectively. Those at minimal risk will be randomized at a ratio of 1:2:3 to high, medium and low-intensity support, respectively.

Randomization will be integrated into the EHR. The Study Nurse who will complete the survey will receive the determination of study arm from an automated program. Both study staff and study participants will be blinded to the designation of minimal/elevated risk stratum.

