STATISTICAL ANALYSIS PLAN

A precision randomized trial to evaluate the impact of tailored hepatitis C virus (HCV) treatment adherence support on HCV treatment outcomes in HIV/HCV co-infected and HCV mono-infected people who inject drugs (PWID) in India

NCT04652804

Supporting Treatment Outcomes among PWID (The STOP-C Study)	
	-
	Funded by:
	onal Institute of Allergy nfectious Diseases
R01-Al-145555-01 Industry Support Provided by:	
Protocol Chair/Co-Chair:	[name] MPH, Co-Chair [name] [name] MPH, Co- Chair
DAIDS-ES Document Number:	DAIDS-ES ID 38666
Version Number:	1.0
Version Day Month Year:	5 January 2024

SIGNATURE PAGE

I agree to conduct the analysis in accordance with the relevant, current protocol.

I agree to personally conduct or supervise the analysis.

Co-Principal Investigator: [name] MPH / Professor

Signed:

Date: 1/5/24

Co-Principal Investigator: [name], PHD MPH / Professor

Signed: Date: 1/5/24

1. Primary outcome

The primary outcome is sustained virologic response (SVR) defined as HCV RNA < lower limit of quantification (LLOQ) 10 – 60 weeks after completion of treatment (cure). The primary analysis will be intention to treat and will be stratified by the risk of treatment failure (minimal and elevated).

The primary analysis will compare the proportion achieving SVR across level of support (low, medium, high intensity) within the two strata of risk (minimal and elevated) independently. Using log-binomial models (or their extensions, i.e., Poisson regression with robust variance estimation) including adjustment for site as a fixed effect, in the elevated risk stratum, we will compare the proportion achieving SVR in those who received the low and moderate intensity interventions (in separate models) to those who received the high intensity intervention resulting in a relative risk (RR). Analysis will be repeated for the minimal risk stratum except comparing those who receive the high and moderate intensity interventions to the low intensity intervention.

Primary comparisons will be intention to treat. That is, the study population for this analysis will include everyone who was randomized. Individuals with missing data on the outcome of interest either due to loss-to-follow-up or death will be treated as failures.

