1a. Per protocol analysis. We will conduct a per protocol analysis which will exclude individuals who died prior to SVR assessment, who are alive but lost to follow-up (i.e., do not complete the SVR visit) and those who prematurely discontinued treatment. The study population for this analysis will include everyone who was randomized, completed a treatment course and completed the SVR evaluation visit.

1b. Sensitivity analyses.

- Regression models will be repeated considering site as a random effect (instead of as a fixed effect).¹
- Regression models will be repeated without adjustment for site.
- To account for covariates that are differentially distributed by arm or prognostic for the outcome:
 - We will repeat the regression models described above adjusting for any baseline demographic and behavioral factors that are significantly different by study arm within strata of risk.
 - We will repeat the regression models described above including a covariate for the prognostic score.
 - We will incorporate the covariates included in the prognostic score through application of the standardized estimator of Moore and van der Laan^{2,3} in the stratified analyses (minimal and elevated). This will allow us to estimate the average treatment effect (ATE) within strata contrasting the proportion of the population that would achieve SVR in the groups of interest.
- To account for missing data/non-adherence related to the primary outcome.
 - Of interest is estimating the most beneficial effect of the higher intensity intervention as if everyone fully complied and there were no losses to follow-up or nonadherence to the intervention. Therefore, missing data will result from persons who do not

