Additional exploratory analyses will evaluate the impact of non-adherence and delays in completing treatment on SVR. Initial analyses will incorporate data from all three arms. Two variables will be calculated: 1) the percentage of doses completed (as described above); and 2) days to treatment completion. While the scheduled course of treatment will be 84 days for most, participants will be instructed to take all of the doses prescribed (even if doses are missed and the total time for treatment completion extends beyond 84 days). In separate models, log-binomial models (or their extensions, i.e., Poisson regression with robust variance estimation) will be used to estimate the association between 1) estimated adherence and SVR; and 2) days to treatment completion and SVR. These analyses will be combined across risk strata and treatment arm but these variables will be included as covariates. Additional analysis will be conducted exclusively among participants assigned to Arm 3 (high intensity support) where weekly adherence data will be collected using biometric data.

3e. Estimation of heterogeneity in treatment effect and estimation of average treatment effect.

Additional analyses will be completed to estimate heterogeneity in treatment effect and the average treatment effect for the primary (SVR) and secondary outcomes defined above.

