The average treatment effect will be determined in order to estimate the effect of the different support strategies in the overall population. Under the unbalanced randomization scenario that is planned, a prognostic score is intentionally created. This score lies between the causal pathway from the individual characteristics to the treatment assignment, thus introducing an "informed confounding", i.e., the causal relationship between treatment assignment and outcome is confounded by the prognostic score (i.e., individual's propensity for treatment failure). To estimate the unbiased, average treatment effect, given that there is information on how the prognostic score affects study arm allocation, the targeted randomization can be used to reweight the sample back to the initial sample as if the randomization allocation was equivalent to all levels of the prognostic score. That is, by using inverse probability of treatment weights, the relationship between the prognostic score and treatment assignment is removed to estimate the average treatment effect to provide answers about whether the high and moderate intensity interventions resulted in superior outcomes in the overall population (i.e., is high intensity support a superior intervention to standard of care in all PWID regardless of propensity for treatment failure?).

Further analyses will seek to use information from the prognostic score and the observed data to identify the optimal threshold for assigning treatment support. That is, by assessing heterogeneity in treatment effect by level of prognostic score, we will potentially be able to identify a range of scores to assist in the decision of whether low, moderate, or high level of support would be most efficacious for individuals based upon the characteristics that determine their prognostic score. First, within the two strata defined by the prognostic score, there remains variability in the prognostic score. Therefore, we will evaluate the impact of the interaction between the prognostic score and the intensity of support received (low, medium and high intensity) on SVR and treatment completion rates in the full sample. The goal of this analysis will be to evaluate the heterogeneity of treatment effect within strata.

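### SAP 3e estimates the overall average treatment effect by weighting alone and names no outcome predictors or variance method: a valid exploratory analysis that probably gives up some precision

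*SAP*

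**What the plan says.** The allocation differs by risk stratum. Protocol 15.5 states: "Those at elevated risk for treatment failure will be randomized at an allocation ratio of 3:2:1 for high, medium and low intensity support respectively". The minimal-risk stratum has the mirror image. A crude overall comparison of arms would therefore be confounded by risk. SAP 3e deals with this by reweighting: "by using inverse probability of treatment weights, the relationship between the prognostic score and treatment assignment is removed to estimate the average treatment effect". Protocol 15.7.2.3 has the same text. Neither gives an outcome model, a site term, baseline covariates or a variance method for this estimate.

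Other parts of the SAP do state such terms. The primary models are fitted "including adjustment for site as a fixed effect". The subgroup models and exploratory analysis 3a also adjust for site. SAP 1b adds the score as a covariate in one sensitivity analysis. In another it applies a standardized, covariate-adjusted estimator, but only inside each stratum: "This will allow us to estimate the average treatment effect (ATE) within strata contrasting the proportion of the population that would achieve SVR". The last part of SAP 3e describes a weighted model with arm, score and their interaction. Its stated purpose is heterogeneity and cut-points, and nothing says that it will be averaged into the overall effect.

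On status, SAP section 3 is the exploratory section, and 3e begins: "Additional analyses will be completed to estimate heterogeneity in treatment effect and the average treatment effect for the primary (SVR) and secondary outcomes defined above". Protocol 15.1 nevertheless lists the overall sample, beside the two strata, among the populations in which efficacy is to be assessed.

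**The concern.** Weighting removes the confounding created by the allocation. It does not use what score and site say about who will reach SVR. Protocol 7.2.3 rests on the premise that the factors in the score influence the outcome, so some unused predictive information is to be expected.

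There is a second, separate gap. Because the variance method is not named, an analyst could use the common robust standard error that treats the weights as fixed. That standard error measures residuals around the overall arm mean, so it counts between-stratum variation in SVR that allocation within strata has already removed.

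At stake is the width of the interval for the programme question in SAP 3e, whether high-intensity support is better for all PWID. Choosing the adjustment after results are seen would also be harder to defend than naming it now.

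**Working it through.** **Inputs from the documents.** Protocol 15.4: "The anticipated sample size for this trial is 3,000 with approximately 420 recruited at each site"; elevated stratum "N=1500 total (750 high intensity, 500 medium intensity, 250 low intensity", with the minimal stratum its mirror image; "assuming a two-sided alpha=0.05 and 80% power"; SVR planning values 0.80 to 0.95. Protocol 15.5: blocked allocation, and AUROC 0.81 for early ART adherence in 119 clients.

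**Assumed inputs (not in the documents).** The AUROC of the score for SVR and the between-site spread in SVR.

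**1. The plan's own figures.** I used the two-proportion formula with pooled null variance and no continuity correction, solved for the RR that gives 80% power. 47 of the 48 cells of Table 15.4.1 match to two decimals. For example, in the elevated stratum at N=1500 and SVR 0.85, high vs low is 1.0755 (stated 1.08) and high vs medium is 1.0621 (stated 1.06). The documents give no precision or power figure for the overall effect.

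**2. Effective size under the weights.** In the high arm, 750 elevated-risk participants have weight 2 and 250 minimal-risk participants have weight 6:

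(750×2 + 250×6)² / (750×4 + 250×36) = 3000² / 12000 = 750.

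The low arm is the same by symmetry. The medium arm has constant weight 3 and keeps 1,000.

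**3. Baseline half-width, high vs low.** With SVR 0.85 and nothing predictive, the variance is 2 × 0.85×0.15/750 = 0.00034, the SE is 1.84 points and the 95% half-width is 3.61 points. Simulation gives 3.62.

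**4. What the fixed-weight SE adds.** Let δ be half the difference in SVR between strata. For the high arm, allocation within strata gives a variance of σ²(elevated)/3000 + σ²(minimal)/1000. The fixed-weight formula adds δ²(1/3000 + 1/1000) = δ²/750. The low arm mirrors this.
- Strata at 80% and 90%: the base variance for the contrast is 0.000333 and the addition is 2×0.0025/750 = 0.0000067, or 2%.
- Strata at 80% and 95%: the base is 0.000277 and the addition is 2×0.005625/750 = 0.000015, or 5%.

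This part comes from the variance formula and is not lost information.

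**5. Adding predictors.** 600 simulated trials per row, N=3000, SVR about 85%, no treatment effect, strata split at the median score. The adjusted estimator is augmented weighting with score, stratum and site. Half-widths and SDs are in percentage points. Ratios are squared quotients of the two preceding columns. The SD columns show the true sampling spread, with weights estimated by stratum to approximate blocked allocation.

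| Assumed predictors | Half-width, weighting (fixed-weight SE) | Half-width, adjusted | Variance ratio | True SD, weighting by stratum | True SD, adjusted | Variance ratio |
|---|---|---|---|---|---|---|
| None | 3.62 | 3.60 | 1.01 | 1.89 | 1.90 | 0.99 |
| AUROC 0.66 | 3.62 | 3.51 | 1.06 | 1.76 | 1.75 | 1.01 |
| AUROC 0.66, site SD 0.6 | 3.63 | 3.45 | 1.11 | 1.85 | 1.83 | 1.02 |
| AUROC 0.80 | 3.59 | 3.23 | 1.24 | 1.74 | 1.65 | 1.11 |
| AUROC 0.80, site SD 0.6 | 3.58 | 3.16 | 1.28 | 1.81 | 1.69 | 1.15 |

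Site SD is on the logit scale. Coverage was 94-96% for weighting and for adjustment. Comparing the two ratio columns, about half or more of the apparent gain comes from replacing a conservative SE.

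**6. Range over score strength.** Excess variance of weighting over adjustment, SVR about 86%, assumed site spread ±0.5 in log-odds:

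| AUROC for SVR | 0.61 | 0.68 | 0.76 | 0.82 |
|---|---|---|---|---|
| Stratum-aware SE | 3% | 6% | 11% | 19% |
| Fixed-weight SE | 5% | 10% | 18% | 32% |

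A further run at SVR about 87%, again in order of rising score strength, gave 3%, 5%, 11%, 19% and 4%, 8%, 18%, 30%.

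**7. High SVR.** At SVR 95% and AUROC 0.61-0.70 the excess is 2-4% (stratum-aware) or 2-5% (fixed-weight). The large-sample half-widths agree: 2.21 falls to 2.19 at AUROC 0.66, where (2.21/2.19)² = 1.02, and to 2.16 with site SD 0.6, where (2.21/2.16)² = 1.05. A strong score (AUROC 0.81) would give 2.09, a fixed-weight ratio of (2.21/2.09)² = 1.12.

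**The case against.** The strongest reply is that nothing is wrong with the planned analysis. It is exploratory, it carries no power target, and its intervals cover correctly. SAP 3e explains how allocation confounding is removed; it is silent on covariates and does not exclude them. The risk stratum already enters through the weights, and the score appears in the heterogeneity model of the same section. SAP 1b also repeats the stratum models without site, so a site-unadjusted stratum result will exist to set beside the overall one. All of this stands, and it limits the weight of the point. It does not remove it, because a plan that names only weighting commits the analyst to nothing more.

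A reader might infer four stronger things that the documents do not support.
- *That the planned overall effect is biased or its error rate wrong.* The weights follow from known allocation probabilities, and simulated coverage is 94-96%.
- *That a quarter or more of the information is discarded.* That size needs both a strong score and a fixed-weight SE. SAP 3e does not specify that SE, and a stratum-aware one removes much of the excess.
- *That the AUROC of 0.81 shows the upper end to be realistic.* It comes from a preliminary model of early ART adherence in 119 clients. Protocol 15.5 calls that outcome a surrogate and expects the algorithm to change.
- *That adjustment recovers the drop from 1,000 to 750 in effective size.* That is the price of the deliberate 3:2:1 and 1:2:3 allocation. It remains after adjustment and does not touch the medium arm.

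**Conclusion.** The point holds as one of efficiency and specification. The overall effect is planned with weighting alone and no stated variance method, while predictors known at entry are left unused.

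For high versus low support at SVR about 85-87%, the excess variance is about 3-19% with a stratum-aware SE and about 4-30% with a fixed-weight robust SE. At SVR 95% with a modest score it is about 2-4%, and it is near zero if neither score nor site predicts SVR. In interval width, the fixed-weight comparison runs from no change to about 12% narrower (3.58 to 3.16 points).

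These sizes rest on equal strata of 1,500, N=3000, and assumed predictive strength of score and site for SVR. Only the direction follows from the protocol's own premise. The stratified primary analysis is unaffected.

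**What to change.** In SAP 3e, name the standardized estimator already cited in SAP 1b as the main method for the overall effect, applied to all randomized participants:
- Model SVR within each arm on risk stratum, continuous score and site, keeping the rule that a missing outcome counts as failure.
- Predict SVR for every participant under each arm, augment with the known allocation probabilities (1/6, 2/6, 3/6), and average.
- Use the influence-function variance.

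Because the allocation probabilities are known, the estimate stays consistent even if the outcome model is wrong. Where nothing predicted SVR, adjustment cost essentially nothing in the simulation (half-width 3.62 against 3.60).

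Keep plain weighting as a sensitivity analysis, with a variance that accounts for allocation within risk strata. SAP 3f reuses the overall analysis by sex, so state a reduced predictor set in case the few female participants cannot support separate site terms.

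The cost is SAP wording and slightly more analysis work. All inputs are already collected at entry, and design and sample size do not change.

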7.2.3. Rationale for the unbalanced allocation approach (precision trial)

Prior trials evaluating the impact of HCV adherence support interventions among PWID have used standard approaches that randomize groups of individuals to different interventions or to a single intervention vs. the standard of care. This approach assumes that all of those assigned to an intervention have the same need for the intervention and the potential to benefit equally from the intervention. However, while the data do support that at least some PWID will need additional support to achieve cure, there are structural barriers (e.g., infrastructure, human capital) that limit the capacity to provide intensive support to all those treated, particularly in settings with high burden.^{31,34} Identifying who can be cured with minimal intervention and who will need more support can potentially improve efficiencies.

This protocol utilizes a "precision" approach to allocating treatment support based on need allowing us to estimate efficacy within strata of risk for treatment failure (minimal/elevated risk) while still allowing estimation of the average treatment effect. This approach is similar to stratified randomization with the modification that treatment allocation is not equal across strata. This targeted randomization actually induces confounding (because the prognostic score is based on factors that influence the outcome) that needs to be accounted for in the analysis (**see Section 15**). However, because of randomization, the factors used in determining propensity for failure will be balanced in expectation, as this is analogous to a propensity score, which balances included covariates. Thus, using a single approach, we can answer multiple questions related to both the efficacy of the support strategy for persons at different levels of risk for failure as well as the impact in the total population of a particular support strategy.

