Of additional interest is identifying the heterogeneous treatment effect of the intensity of support received on SVR and secondary outcomes across the *entire distribution of* prognostic score (note that the prognostic score will be continuous). Therefore, by using the weighted (by inverse probability of treatment weights) study sample, the interaction between the prognostic score and intensity of support received on SVR and treatment completion rates can be examined across the

entire study population. Specifically, a model will include the indicator variables for level of support, the main effect of the prognostic score, and the interaction term. The model will allow for non-linear relationship between prognostic score and outcomes and depict the estimated treatment effect graphically to determine the optimal cut-points of the prognostic score to assign low, medium and high intensity treatment support to maximize SVR.

3f. Effect of heterogeneity of intervention effect by sex assigned at birth.

It is of interest to examine whether the impact of the intervention varies by sex assigned at birth. We anticipate that power will be limited in these analyses since in many of the field sites, the number of participants who were assigned female sex at birth is negligible, consistent with the epidemiology of injection drug use in India. However, we will conduct stratified analyses to explore whether the effect of the level of treatment support varies by sex assigned at birth within strata of treatment nonadherence risk. We will also conduct the analyses of the average treatment effect stratified by sex assigned at birth.

REFERENCES

- **3.** Moore KL, van der Laan MJ. Covariate adjustment in randomized trials with binary outcomes: targeted maximum likelihood estimation. *Stat Med* 2009;28:39-64.

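### SAP 3e picks score cut-points solely to maximise SVR, with no step to separate a real crossing of the fitted curves from a chance one and no correction for evaluating the rule on the data that chose it

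*SAP*

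**What the plan says.** SAP 3e plans an analysis in the full sample, reweighted by the inverse probability of assignment, in which "a model will include the indicator variables for level of support, the main effect of the prognostic score, and the interaction term". The score is kept on its full scale ("note that the prognostic score will be continuous"), non-linear effects are allowed, and the estimated treatment effect is drawn against the score. The stated use of the picture is "to determine the optimal cut-points of the prognostic score to assign low, medium and high intensity treatment support to maximize SVR". The preceding text asks whether a "low, moderate, or high level of support would be most efficacious for individuals". Protocol 15.7.2.3 has the same wording.

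The reason for tailoring is given in Protocol 7.2.3: capacity limits prevent intensive support for everyone, and "Identifying who can be cured with minimal intervention and who will need more support can potentially improve efficiencies". Protocol 7.2.4 places cost analyses in the parent grant. SAP 1c has a 5% non-inferiority margin for the minimal-risk stratum. Neither is linked to 3e.

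SAP 3e gives no minimum gain or tolerance, no requirement that the interaction be supported, no interval for a cut-point, and no validation of the resulting rule.

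**The concern.** There are two separate problems.

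First, the rule takes whichever arm has the highest fitted SVR, and nothing in 3e asks whether the curves differ by more than chance. Three arms estimated along a continuous score will often cross somewhere, particularly where an arm is small. The allocation makes the high arm smallest at low scores and the low arm smallest at high scores. Reading the SVR under the rule from the same fit then overstates it, because the rule was chosen to make that fitted value as large as possible.

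Second, maximising SVR does not address the stated purpose of finding who can do well with less. Someone for whom low and high support work equally well is a tie, and someone who gains a trivial amount is assigned high.

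At stake is the interpretation of the exploratory thresholds. Protocol 15.1 says the trial results are to guide programmes, and 3e is where score thresholds for assigning support would come from.

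**Working it through.** **Inputs from the documents.** Protocol 15.4: "The anticipated sample size for this trial is 3,000", about 1500 per stratum at a median split. Protocol 15.5: elevated-risk participants are "randomized at an allocation ratio of 3:2:1 for high, medium and low intensity support respectively". The minimal-risk stratum reverses this, 1:2:3 in the same arm order. This gives 750/500/250 (high/medium/low) in the elevated stratum and 250/500/750 in the minimal stratum.

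**The plan's own figure.** No figure is given for the cut-point analysis. The nearest is the worked example in Protocol 15.4: elevated risk, n=1500, comparator SVR 85%, two-sided alpha 0.05, power 80%. Solving the two-proportion power equation (pooled variance under the null) for the relative risk gives 1.062 for high versus medium (750 v 500) and 1.075 for high versus low (750 v 250). These round to the stated 1.06 and 1.08. In points, 0.85 × 0.06 = 5.1 and 0.85 × 0.08 = 6.8.

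**Noise for a whole stratum.** At SVR 85%, SE(high − low) = √[0.85 × 0.15 × (1/750 + 1/250)] = √(0.1275 × 0.00533) = 0.026, or 2.6 points. The difference at a single score uses less information than the whole stratum, so it is noisier.

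**The logic.** Let p_a(s) be SVR in arm a at score s. The stated rule is d(s) = the arm with the largest p_a(s). If p_high(s) exceeds both others at every s, then d(s) = high everywhere and no cut-point exists. The fitted rule departs from this only where a fitted curve for low or medium lies above the fitted curve for high.

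**Simulation.** N=3000, allocation as above, weights 1/P(arm | stratum), a weighted logistic model with a 3-knot spline of the score per arm, and the arm with the highest fitted SVR taken on a 97-point grid. *Assumed, not in the documents:* logistic link, uniform score, low-arm SVR falling from 90% to 70%, and the effect sizes shown. The taking of the pointwise maximum is a literal reading of the aim; the SAP specifies only a graph.

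| True benefit, medium / high (points, all scores) | Score range assigned below high, spline | Same, linear score |
|---|---|---|
| +1.5 / +3 | about 37% | about 28% |
| +3 / +6 | about 16% | about 10% |
| +4.5 / +9 | about 4% | about 3% |

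These shares move by a few points between runs. With +1.5/+3 and the spline, the apparent gain over high for all is +0.7 to +0.8 points, while the true change is −0.7 to −0.8. With no arm effect, the apparent gain is +1.9 to +2.0 points and the truth is 0.

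**Is it sampling error?** A second set used a low-arm SVR of 95% falling to 80% and counted the runs that gave any cut-point (linear / spline).
- +1/+2 points everywhere: 75% / 96% at N=3000, and 3% / 7% at N=300,000.
- +3/+6 points everywhere (capped at 99.5%): 40% / 61% at N=3000, and 0% / 0% at N=300,000.

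The cut-points almost vanish as N grows, so in these settings they are sampling error.

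**When the boundary is real.** With a true crossover (high −4 points at lowest risk to +6 at highest, true cut 0.40), the cut-point persists at N=300,000: median 0.46 linear, 0.38 spline.

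**The case against.** A reader might infer that every cut-point found this way is noise. The documents do not support that. More support never lowering SVR does not rule out a boundary: if the gain is zero below some score and positive above it, low support also attains the maximum below it. SAP 1c raises the possibility of no added benefit in the minimal-risk stratum. Nor is monotone benefit guaranteed. Protocol 7.2.2 notes that extra support might prove a burden, and the minimal-risk hypothesis in 15.3.1 does not order high against medium. This stands, and it is why the point is conditional. It does not remove the need for the missing step, because 3e cannot tell a real crossing from a chance one in either case.

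A reader might also infer that the plan cannot show low support to be adequate for anyone. SAP 1c tests non-inferiority in the minimal-risk stratum if superiority is not shown there. That covers the stratum as a whole; it sets no cut-point and does not feed 3e.

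A third tempting reading is that the trial will issue these cut-points as a triage rule. Section 3 of the SAP is headed exploratory, and 3e speaks of potentially identifying a range of scores to assist a decision. Nothing commits the sponsor to publish or apply a rule.

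Finally, the simulated size depends on assumed curves, and the largest figure comes from a benefit (+3 points) below the design's detectable differences of 5.1 to 6.8 points. This stands: the share falls to about 4% at +4.5/+9, and the true SVR loss across these settings is modest, about 0.2 to 0.8 points.

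**Conclusion.** The concern holds in conditional form. SAP 3e chooses cut-points by fitted SVR alone, with no safeguard against chance crossings and no correction for optimism. Where more support truly raises SVR at every score, fitted cut-points are mostly sampling error. The share of the score range wrongly placed below high runs from about 37% to about 4% as the uniform benefit rises from +1.5/+3 to +4.5/+9 points. With equal arms, the rule appears to gain about 2 points over high for all when the truth is 0.

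The percentages rest on the assumed score distribution, SVR curve, link and effects, and on reading the maximum off point estimates. The logical point does not depend on them. The primary and secondary results are unaffected. The change is worth making because 3e is the only place where the plan derives score thresholds for assigning support.

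**What to change.** Amend SAP 3e as follows, and align Protocol 15.7.2.3.

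1. Report a cut-point only when the score-by-arm interaction supports it, under a criterion stated in advance. Otherwise report 'no cut-point supported'. An interaction can exist without a crossing, so item 2 is needed as well.
2. Give a confidence band for each arm difference across the score and an interval for each cut-point.
3. Report SVR under the rule, compared with high for all, after bootstrap or leave-one-site-out correction, with the rule re-chosen in each resample or fold. Protocol 15.5 already uses site-wise splitting to build the score.
4. Beside the SVR-maximising rule, add one that serves the purpose in Protocol 7.2.3: the least intensive arm whose SVR is shown, by the confidence limit and not the point estimate, to lie within a pre-set tolerance of the best arm.

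The comparison in item 4 must be with the best arm, not the next intensity. With true steps of 4.5 and 4.5 points, each step is under 5, so a 5-point next-step rule gives low to all at the truth and forgoes 9 points. In simulation it lost about 6.5 points, against 0.2 for maximising SVR. The sponsor should set the tolerance; the 5% in SAP 1c was stated for the minimal-risk stratum and should not carry over automatically to the rest of the score.

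Such a rule has a real target, but an imprecise one. With assumed low-arm SVR of 95% falling to 75%, a high-arm benefit rising from 0 to 14 points (medium 0 to 6) and an illustrative 5-point tolerance applied to point estimates, the low zone truly ends at 5/14 = 0.36. At N=3000 the spline estimate has median 0.31 (10th to 90th percentile 0.09 to 0.54), which shows why an interval is needed.

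Cost: SAP wording, modest extra analysis and no new data. The sponsor must name a tolerance in advance and accept a greater chance of reporting no cut-point.
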